9.4.5.3. Chest Radiography

Posterior-anterior (PA) chest x-ray (CXR) will be obtained at screening (Visit 1) unless, in the opinion of the investigator or based on local standard of care, both PA and lateral views are indicated.

A CXR does not have to be performed if the patient has had a CXR that is sufficient for TB evaluation according to local standard of care within 3 months of screening, and the CXR film(s) or a radiology report is available to the investigator for review.

9.4.5.4. Hepatitis B Screening

Patients who test HBsAg+, test HBcAb+ in conjunction with positive confirmatory HBV DNA test, or have positive HBV DNA test, regardless of HBsAb status, at screening will be excluded.

Any enrolled patient who is HBcAb+ will undergo periodic monitoring of HBV DNA as per the Schedule of Activities (Section 2).

In addition to the above, any enrolled patient who is HBcAb+ and who experiences an elevated ALT or AST level >3x ULN must undergo HBV DNA testing. If the HBV DNA test is negative, the investigator should consult with the Lilly-designated medical monitor regarding further management of the patient.

If the result of the HBV DNA test is positive but below quantification, study drug should be withheld and a repeat test done immediately. The Lilly-designated medical monitor should be contacted regarding study status of the patient. If the result of the HBV DNA test is positive and quantifiable, the patient must be discontinued from the study and should receive appropriate follow-up medical care, including consideration for antiviral therapy. A specialist physician in the care of patients with hepatitis (for example, infectious disease or hepatologist subspecialists) should be consulted, and the patient should potentially be started on antiviral therapy prior to discontinuation of any immunosuppressant therapy (including study drug). Timing of discontinuation from the study treatment, the study, and of any immunosuppressant therapy (including study drug) needs to be based on the recommendations of the consulting specialist physician in conjunction with the investigator and medical guidelines/standard of care.

9.4.5.5. Hepatitis C Screening

Patients who test positive for HCV antibody and have a positive confirmatory HCV RNA test at screening will be excluded.

Patients with a previous diagnosis of hepatitis C who have been treated with antiviral therapy and achieved a sustained virologic response may be eligible for inclusion in the study, provided they have no detectable RNA on the screening HCV RNA test for this protocol. A sustained virologic response is defined as an undetectable HCV RNA level, 12 weeks after completion of a full, documented course of an approved antiviral therapy for HCV.

Patients who have spontaneously cleared HCV infection, defined as (i) a positive HCV antibody test and (ii) a negative HCV RNA test, with no history of anti-HCV treatment, may be eligible for inclusion in the study, provided they have no detectable HCV RNA on screening for this study.

Any patient with a history of HCV infection who develops elevated ALT >3xULN will be tested for HCV RNA.

Anyone diagnosed with hepatitis C during the study will be discontinued from the study and should receive appropriate follow-up medical care.

9.4.6. Safety Monitoring

Lilly will periodically review evolving aggregate safety data within the study by appropriate methods.

In the event that safety monitoring uncovers an issue that needs to be addressed by unblinding at the group level, members of the DMC, consisting of members external to Lilly (see Section 10.3.8), and/or the Lilly Global Patient Safety (GPS) Safety Internal Review Committee (SIRC), consisting of GPS reviewers outside the study team, when appropriate, can view unblinded data and conduct additional analyses of the unblinded safety data. The SIRC and the GPS expedited reporting team can also unblind at the individual SAE case level, when appropriate.

9.4.6.1. Hepatic Safety Monitoring

If a study patient experiences elevated ALT ≥ 3 x ULN, ALP ≥ 2 x ULN, or elevated TBL ≥ 2 x ULN, liver testing (Appendix 6) should be repeated within 3 to 5 days including ALT, AST, ALP, TBL, direct bilirubin, gamma-glutamyl transferase, and creatine kinase to confirm the abnormality and to determine if it is increasing or decreasing. If the abnormality persists or worsens, clinical and laboratory monitoring should be initiated by the investigator and in consultation with the study medical monitor. Monitoring of ALT, AST, TBL, and ALP should continue until levels normalize or return to approximate baseline levels.

Hepatic Safety Data Collection

Additional safety data should be collected via the eCRF if 1 or more of the following conditions occur:

- Elevation of serum ALT to ≥ 5 x ULN on 2 or more consecutive blood tests
- Elevated serum TBL to ≥ 2 x ULN (except for cases of known Gilbert's syndrome)
- Elevation of serum ALP to ≥ 2 x ULN on 2 or more consecutive blood tests
- Patient discontinued from treatment due to a hepatic event or abnormality of liver tests
- Hepatic event considered to be a SAE

9.5. Pharmacokinetics

At the visits and times specified in the Schedule of Activities (Section 2), venous blood samples will be collected to determine the serum concentrations of mirikizumab.

Instructions for the collection and handling of blood samples will be provided by the Sponsor. The actual date and time (24-hour clock time) of each sampling will be recorded.

Drug concentration information that may unblind the study will not be reported to investigative sites or blinded personnel.

Bioanalytical samples collected to measure investigational product concentration will be retained for a maximum of 1 year following last patient visit for the study.

9.6. Pharmacodynamics

Not applicable.

9.7. Pharmacogenomics

9.7.1. *Whole Blood Sample for Pharmacogenetic Research*

A whole blood sample will be collected for pharmacogenetic analysis as specified in the Schedule of Activities (Section 2) where local regulations allow.

Samples will not be used to conduct unspecified disease or population genetic research either now or in the future. Samples will be used to investigate variable response to mirikizumab and to investigate genetic variants thought to play a role in psoriasis. Assessment of variable response may include evaluation of AEs or differences in efficacy.

All samples will be coded with the patient number. These samples and any data generated can be linked back to the patient only by the investigator site personnel.

Samples will be retained at a facility selected by Lilly or its designee for a maximum of 15 years after the last patient visit for the study, or for a shorter period if local regulations and/or ERBs/investigational review boards impose shorter time limits. This retention period enables use of new technologies, response to regulatory questions, and investigation of variable response that may not be observed until later in the development of mirikizumab or after mirikizumab becomes commercially available.

Molecular technologies are expected to improve during the 15-year storage period and therefore cannot be specifically named. However, existing approaches include whole genome or exome sequencing, genome wide association studies, and candidate gene studies. Regardless of the technology utilized, genotyping data generated will be used only for the specific research scope described in this section.

CCI

CCI [REDACTED]

[REDACTED]

9.9. Medical Resource Utilization and Health Economics

Health Economics and Medical Resource Utilization parameters will not be evaluated in this study.

10. Statistical Considerations

10.1. Sample Size Determination

Approximately 500 patients will be randomized at a 4:1 ratio in the blinded Induction Period to receive 250 mg mirikizumab or placebo SC at Weeks 0, 4, 8, and 12. Stratified block randomization will be performed with the following stratification factors: previous exposure to biologic therapy (yes/no), body weight (<100 kg or ≥100 kg), and geographic region (North America or Other).

There are multiple primary endpoints in this study: sPGA (0,1) and PASI 90 at Week 16. The assumed sPGA (0,1) responses are 70% for the mirikizumab arm and 5% for the placebo arm. The assumed PASI 90 responses are 70% for the mirikizumab arm and 3% for the placebo arm. These assumptions are based upon the results of the mirikizumab Phase 2 Study AMAF (Reich et al. 2017b) and review of historical clinical studies in psoriasis (Langley et al. 2014; Gordon et al. 2016; Blauvelt et al. 2017; Papp et al. 2017; Reich et al. 2017a).

With a total sample size of 500 patients, randomizing 400 patients to the mirikizumab arm and 100 patients to the placebo arm, this study has power of >95% for testing superiority of mirikizumab to placebo based on a 2-sided chi-square test with alpha of 5% on sPGA(0,1). It also provides a power of >95% for testing superiority of mirikizumab to placebo on PASI 90 based on a 2-sided chi-square test with alpha of 5%.

In order to account for multiple testing for the comparisons of 2 mirikizumab groups against the placebo group in the Maintenance Period, a 2-sided chi-square test at the 0.025 level is assumed. Assuming 70% of the mirikizumab patients are re-randomized in the Maintenance Period at Week 16 (Visit 7) at a 1:1:1 ratio to 250 mg mirikizumab Q8W, 125 mg mirikizumab Q8W or placebo, approximately 93 patients will be included in each treatment group. Stratified block randomization will be performed with the stratification factor of body weight at baseline (<100 kg or ≥100 kg). This sample size will provide >95% power to test the difference in the proportion of patients maintaining PASI 90 from Week 16 (Visit 7) after re-randomization at the start of the Maintenance Dosing Period to Week 52 (Visit 16) between each mirikizumab dosing interval and placebo, assuming the proportions of patients maintaining PASI 90 are 80% for 250 mg mirikizumab Q8W, 70% for 125 mg mirikizumab Q8W, and 10% for placebo.

10.2. Populations for Analyses

For purposes of analysis, the following populations are defined:

Population	Description
Induction ITT	All randomized patients, even if the patient does not take the assigned treatment, does not receive the correct treatment, or otherwise does not follow the protocol. Patients will be analyzed according to the treatment to which they were assigned. Unless otherwise noted, efficacy and health outcomes analyses for the Induction Period will be conducted on this population.
Induction Safety	All randomized patients who received at least 1 dose of the study treatment. Patients will be analyzed according to the treatment to which they were assigned. Safety analyses for the Induction Period will be conducted on this population.
Re-randomized Maintenance ITT	All ITT patients who received at least 1 induction dose of the study treatment and have been re-randomized at Week 16. Efficacy and health outcomes analyses for the Maintenance Period will be conducted on this population.
Re-randomized Maintenance Safety	All ITT patients who received at least 1 induction dose of the study treatment, have been re-randomized at Week 16, and have received at least 1 maintenance dose. Safety analyses for the Maintenance Period will be conducted on this population.

Abbreviation: ITT = intent-to-treat.

Additional analysis populations will be described in the SAP as deemed appropriate.

10.3. Statistical Analyses

10.3.1. General Statistical Considerations

Statistical analysis of this study will be the responsibility of Lilly or its designee.

Any change to the data analysis methods described in the protocol will require an amendment ONLY if it changes a principal feature of the protocol. Any other change to the data analysis methods described in the protocol, and the justification for making the change, will be described in the clinical study report (CSR). Additional exploratory analyses of the data will be conducted as deemed appropriate.

Efficacy analysis for induction outcomes will be conducted on the Induction intent-to-treat (ITT) population, while efficacy analysis for the maintenance outcomes will be conducted on the re-randomized maintenance population as defined in Section 10.2. The induction and maintenance safety analysis will be performed on the induction safety and re-randomized maintenance safety populations, respectively. Additional safety and efficacy analysis of the patients who are not re-randomized for the maintenance portion of the study will be defined in the SAP.

Continuous data will be summarized in terms of the mean, standard deviation, minimum, maximum, median, and number of observations. Categorical data will be summarized as frequency counts and percentages. Unless otherwise specified, all hypothesis tests will be 2-sided with alpha of 0.05. Multiple testing will be controlled as described in Section 10.3.1.2.

Unless otherwise specified, baseline for efficacy and health outcomes endpoints during both the Induction and Maintenance Periods will be defined as the last available value before the initial randomization during the Induction Period, which in most cases will be the measure recorded at Week 0 (Visit 2). Detailed definitions of baseline for safety-related analyses will be described in the SAP.

Unless otherwise specified, the statistical analysis models for the Induction Period will adjust for the covariates: previous exposure to biologic therapy (yes/no), body weight (<100 kg or ≥100 kg), and geographic region (North America or Other). Similarly, unless otherwise specified, the statistical analysis models for the Maintenance Period will adjust for the covariate body weight (<100 kg or ≥100 kg).

For assessments of the primary endpoints and other categorical efficacy and health outcomes endpoints, the Cochran–Mantel–Haenszel (CMH) chi-square test will be used to compare the treatment groups with the stratification factors mentioned above. The CMH chi-square p-value will be provided. In addition, the absolute treatment difference in proportions will be provided along with the 95% 2-sided confidence interval estimate.

Treatment comparisons of continuous efficacy and health outcome variables with multiple post-baseline measurements will be made using mixed-effects model for repeated measures (MMRM). When MMRM is used, the model includes treatment, baseline value, visit, the interaction of treatment-by-visit as fixed factors, and the induction/maintenance covariates mentioned above. The covariance structure to model the within-patient errors will be unstructured. If the unstructured covariance matrix results in a lack of convergence, the heterogeneous Toeplitz covariance structure, followed by the heterogeneous autoregressive covariance structure will be used. The Kenward-Roger method will be used to estimate the denominator degrees of freedom. Type III tests for the least squares means will be used for the statistical comparison; the 95% confidence interval will also be reported.

Treatment comparisons of continuous efficacy and health outcome variables with a single post-baseline time point will be made using analysis of covariance (ANCOVA) with the following in the model: treatment group, baseline value, and Induction Period/Maintenance Period covariates mentioned above. Type III tests for least-square (LS) means will be used for statistical comparison between treatment groups. The LS mean difference, standard error, p-value, and 95% confidence interval, unless otherwise specified, will also be reported. Missing data imputation method for ANCOVA model will be specified in the SAP.

Fisher's exact test will be used for categorical safety data including AEs, unless otherwise specified. Continuous safety data including vital sign and laboratory values will be analyzed using ANCOVA with treatment and baseline value in the model, unless otherwise specified. Also, laboratory analytes will be presented as mean changes from baseline and as incidence of shift between normal and abnormal states.

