6.1.3. Definition of Study Baseline

For efficacy and health outcomes, study baseline is defined as the last non-missing assessment (including unscheduled visits) before the first injection, which in most cases will be the measure recorded at Week 0 (Visit 2). For efficacy/health outcome measures, if the patient does not take any injection, the last available value on or prior to the randomization date will be used. In cases where baseline measurements are taken on the same day as the injection, the baseline measurements are used as the baseline for data analysis.

For the Psoriasis Symptom Scale (PSS), the weekly average of at least 4 days of the consecutive 7 days prior to the first injection (or randomization, if the patient does not take any injection) will be the study baseline score.

Baseline for safety analysis is described in the Safety section (Section 6.13).

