In addition, when specified as a sensitivity analysis, pseudo-likelihood-based mixed-effects model of repeated measures (Categorical MMRM) estimating the percentage of patients achieving response across postbaseline visits may be used. When MMRM is used, the model includes treatment, baseline value (continuous), visit, the interaction of the baseline value-by-visit, the interaction of treatment-by-visit, and the induction/maintenance covariates mentioned in Section 6.2 as fixed factors. The binomial distribution and the logit link function will be used. The residual pseudo-likelihood with a subject-specific expansion (RSPL) will be used, which is equivalent to restricted maximum likelihood (REML). An unstructured covariance matrix will be used to model the within-patient variance-covariance errors. If the unstructured covariance matrix results in a lack of convergence, the heterogeneous Toeplitz covariance structure, followed by the heterogeneous autoregressive covariance structure will be used. The Kenward-Roger approximation will be used to estimate the denominator degrees of freedom. The Newton-Raphson with ridging optimization technique will be used to aid with convergence. The probability of response, the corresponding 2-sided 95% CI, and the p-value for the treatment comparisons at postbaseline visits will be reported.

Treatment comparisons of continuous efficacy and health outcome variables with multiple postbaseline measurements will be made using mixed-effects model for repeated measures (MMRM). When MMRM is used, the model includes treatment, baseline value, visit, the interaction of the baseline value-by-visit, the interaction of treatment-by-visit, and the induction/maintenance covariates mentioned in Section 6.2 as fixed factors. The covariance structure to model the within-patient errors will be unstructured. If the unstructured covariance matrix results in a lack of convergence, the heterogeneous Toeplitz covariance structure, followed by the heterogeneous autoregressive covariance structure will be used. The restricted maximum likelihood (REML) will be used. The Kenward-Roger method will be used to estimate the denominator degrees of freedom. Type III tests for the least squares (LS) means will be used for the statistical comparison; the 95% confidence interval will also be reported.

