Treatment comparisons of continuous efficacy and health outcome variables with a single postbaseline time point will be made using analysis of covariance (ANCOVA) with the following in the model: treatment group, baseline value, and Induction Period/Maintenance Period covariates mentioned in Section 6.2. Type III tests for LSMeans will be used for statistical comparison between treatment groups. The LSMean difference, standard error, p-value, and 95% CI, unless otherwise specified, will also be reported. Analysis of covariance may also be used in addition to the MMRM approach, by repeating analysis for each time point.

The Kaplan-Meier (KM) product limit method will be used to estimate the survival for several time to event analyses. The hazard ratio and log-rank test stratified by covariates mentioned in Section 6.2 will be reported. Time for all analysis will be described in units of weeks.

For variables that are not collected at each postbaseline visit, data may exist at visits where the variable was not scheduled to be collected. In these situations, data from the early discontinuation visit that do not correspond to the planned collection schedule will be excluded from the MMRM analysis (Andersen and Millen 2013). For by-visit summaries/displays, such as boxplots, the weeks when data was not scheduled to be collected may not be displayed. However, unscheduled assessments within any defined study period will still be used in the shift analyses, and for imputing values for the change from baseline to modified baseline observation carried forward (mBOCF) endpoint analyses.

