6.2. Adjustments for Covariates

Unless otherwise specified, the statistical analysis models for the Induction Period efficacy will include adjustment for the covariates: previous exposure to biologic therapy (yes/no), body weight (<100 kg or ≥100 kg), and geographic region (North America or Other). In all models, the adjustment for covariates will be performed by coding each of 8 possible combinations of the covariates as a separate strata, and the strata will be actual the variables adjusted for. Similarly, unless otherwise specified, the statistical analysis models for the Maintenance Period efficacy will adjust for the covariate body weight (<100 kg or ≥100 kg). These covariates correspond to the stratification factors to be used during randomization. When MMRM or ANCOVA is used, additional covariates, such as baseline, will be used, as described in Section 6.1.4.

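### Maintenance MMRM and ANCOVA models leave out the pre-dose Week 16 value, giving up some precision in supportive continuous analyses

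*Protocol*

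**What the plan says.** - **Baseline.** Protocol 10.3.1 uses one baseline for both periods: for efficacy and health outcomes, it "during both the Induction and Maintenance Periods will be defined as the last available value before the initial randomization during the Induction Period". SAP 6.1.3 is in line: "study baseline is defined as the last non-missing assessment (including unscheduled visits) before the first injection". Neither document defines a separate efficacy baseline for the Maintenance Period.
- **MMRM.** In SAP 6.1.4, "the model includes treatment, baseline value, visit, the interaction of the baseline value-by-visit", then treatment-by-visit and the stratification covariates.
- **ANCOVA.** SAP 6.1.4 lists "treatment group, baseline value, and Induction Period/Maintenance Period covariates mentioned in Section 6.2".
- **Covariates.** SAP 6.2 states that "the statistical analysis models for the Maintenance Period efficacy will adjust for the covariate body weight" and adds: "When MMRM or ANCOVA is used, additional covariates, such as baseline, will be used, as described in Section 6.1.4". That baseline is the Week 0 value.
- **Timing of Week 16.** Under the Schedule of Activities (footnote a), assessments come before dosing. SAP Table AMAK.6.3 starts the Maintenance Period at Week 16 dosing. The Week 16 value therefore precedes the re-randomized treatment and is not a maintenance outcome row either.
- **Contrast within the SAP.** For maintenance laboratory data, SAP 6.13.4 takes the last Induction Period measurement as baseline.

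**The concern.** The maintenance comparison rests on a second randomization, and the natural covariate for it is disease state at that moment. The Week 0 value lies on the far side of 16 weeks of active treatment. For many scales it probably says less about Week 52 than the Week 16 value does.

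SF-36 shows this most plainly. It is scheduled only at Weeks 0, 16 and 52, and its maintenance analysis is an ANCOVA at the last visit. The one scheduled measurement in between is not used.

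At stake are wider confidence intervals than necessary for the continuous maintenance analyses in SAP Table AMAK.6.6, with about 93 patients per arm or fewer on scales limited to a subgroup.

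**Working it through.** **The plan's own figure.** The only maintenance power statement concerns PASI 90 at Week 52 (Protocol 10.1, SAP 5.1).
- Patients per arm: 400 × 0.70 / 3 = 93.3, or about 93.
- At two-sided alpha 0.025, power is above 99.9% for 80% versus 10% and for 70% versus 10%. The stated figure of more than 95% is reproduced.
- About 12 and 17 patients per arm would already give 95% power.
- SAP 6.10.3 analyses this endpoint by CMH with NRI. No MMRM or ANCOVA enters, so the omitted covariate does not touch it.

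The documents give no power or precision figure for the maintenance MMRM or ANCOVA.

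**Inputs for the gain.** No correlations are given, so these are assumptions: Week 0 to Week 16, 0.3; Week 0 to Week 52, 0.2; Week 16 to Week 52, r = 0.3 to 0.6.

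**Without selection, same correlation in every arm.** The partial correlation of Week 16 with Week 52 given Week 0 is

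p = (r − 0.3 × 0.2) / √[(1 − 0.3²)(1 − 0.2²)] = (r − 0.06) / 0.935,

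and adding Week 16 multiplies the variance of a treatment difference by 1 − p².

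| r | p | 1 − p² | Simulation, 93 per arm |
|---|---|---|---|
| 0.3 | 0.257 | 0.934 | 0.94 |
| 0.4 | 0.364 | 0.868 | 0.87 |
| 0.5 | 0.471 | 0.778 | 0.77 |
| 0.6 | 0.578 | 0.666 | 0.67 |

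The variance falls by about 6 to 33%. The standard error falls by 1 − √0.934 = 3% up to 1 − √0.666 = 18%.

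**With responder selection.** Only PASI 90 responders are re-randomized. Keeping the best 70% on the Week 16 value itself gives variance ratios of 0.97 at r = 0.3 and 0.87 at r = 0.5 (r taken before selection), a fall of 3 to 13%. This is the relevant case for PASI.

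**With a weak correlation on placebo.** Let the Week 16 to Week 52 correlation be 0.1 on placebo (also assumed) and r in both mirikizumab arms, without selection. With a common slope across the three arms, the fitted slopes are those for the average correlation (2r + 0.1)/3. Averaging the residual variances of one mirikizumab arm and placebo, and dividing by 1 − 0.2² = 0.96, gives 0.98, 0.96, 0.94 and 0.91 for r = 0.3, 0.4, 0.5 and 0.6. A simulation at 93 per arm gave 0.98, 0.96, 0.96 and 0.89. The fall is about 2 to 11%, and the upper end is nearer 9% by formula.

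**If Week 16 adds nothing.** The simulated variance ratio is about 1.005, a loss of about 0.5%.

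**The case against.** The strongest reply is that nothing here is an error. Treatment is re-randomized at Week 16, so a model with the Week 0 value and the weight stratum gives an unbiased comparison with a valid error rate. Chance imbalance at Week 16 is already reflected in the standard error. That stands. A reader might infer that the maintenance results are biased, or that the Week 52 confirmatory claim is weakened; the documents support neither.

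The analyses concerned are also supportive only. Apart from the pharmacokinetic items, the protocol-defined maintenance endpoints (time to relapse, relapse, PASI 90, rebound, regained PASI 90) are binary or time-to-event. The protocol-listed change scores belong to the first 16 weeks. The maintenance change scores appear only in SAP Table AMAK.6.6, and SAP Section 4 calls analyses of endpoints outside the protocol supportive. This stands too.

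The size is uncertain, and the upper end of the range is favourable:
- The 33% figure needs a high correlation in every arm and no selection. Placebo is assumed to hold PASI 90 in only 10%, and SAP 6.3.2 drops visits after relapse from the MMRM.
- BSA does not escape the selection. Area is a multiplier in PASI, so PASI 90 narrows Week 16 BSA as well.
- PSS is a weekly diary mean up to Week 16 and a single office score afterwards, so covariate and outcome are measured differently.
- Some scales have fewer than 93 per arm: NAPSI needs nail involvement at baseline, and WPAI-PSO needs employment. A covariate with missing values and no rule for them would drop patients.

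These limits reduce the gain and shape the fix. They do not remove the case for using a value that is already collected and unaffected by the maintenance assignment. The narrow Week 16 range among responders applies directly to PASI and BSA, but not to scales that play no part in the selection.

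**Conclusion.** The point holds as a modest efficiency gain. Both documents omit the Week 16 value from the maintenance MMRM and ANCOVA, and adding it would introduce no bias.

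The range runs from almost nothing to about a third of the variance, and every figure in it rests on assumed correlations. The gain is likely smallest for PASI and BSA, and larger for NAPSI, DLQI, SF-36, WPAI-PSO and EQ-5D, except where a scale is near its floor at Week 16. No confirmatory conclusion depends on it.

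**What to change.** Amend SAP 6.1.4 and 6.2 before the Week 52 unblinding. For continuous efficacy and health-outcome analyses in the Re-randomized Maintenance ITT population:

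- Add the last pre-dose value up to Week 16 as a covariate, alongside the Week 0 value and the weight stratum. Include its visit interaction in the MMRM; the ANCOVA needs no interaction.
- Keep change from Week 0 as the outcome. With the Week 0 value in the model, reporting is unchanged.
- For PSS, use the Week 16 weekly diary mean from SAP Appendix 1.
- State a rule that keeps patients with a missing Week 16 covariate in the analysis, for example the last available induction value, or single mean imputation with a missing indicator.

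Protocol 10.3.1 sets its baseline and covariates unless otherwise specified and requires an amendment only for a principal feature, so SAP wording should be enough. The cost is a few degrees of freedom, about 0.5% of variance if Week 16 adds nothing, and the missing-covariate rule.
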